### **11.2.2 Treatment-Emergent Laboratory Abnormalities**

Treatment-emergent laboratory abnormalities are defined as values that increase by at least 1 toxicity grade from baseline at any postbaseline time point, up to and including the date of last dose of study treatment plus 30 days. If the relevant baseline laboratory value is missing, any abnormality of at least grade 1 observed within the time frame specified above will be considered treatment-emergent.

Treatment-emergent laboratory abnormalities will be summarized for the selected laboratory parameters.

## **11.3 Exposure to Concomitant Medication, and Subsequent anti-NPC Therapy**

The number (%) of subjects who received each concomitant medication will be summarized by preferred term as coded by the World Health Organization Drug (WHODRUG) dictionary. The number (%) of subjects who receive subsequent anti-NPC therapies will also be summarized if data are available.

**Concomitant medication:** A concomitant medication is any medication except study treatment taken during the treatment period. All medications will be considered as concomitant medication unless

- The complete or partial medication start date is clearly after the last dose of study treatment

or

- The complete or partial medication end date is clearly before the first dose date of study treatment

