5.3 Prior and Concomitant Medications/Therapies

5.3.1 *Permitted Medications/Therapies*

All treatments that the investigator considers necessary for a subject's welfare may be administered at the discretion of the investigator in keeping with the community standards of medical care; however, refer to prohibited medications and therapies in Section 5.3.1.1. All concomitant medication will be recorded, including all prescription, over-the-counter, herbal supplements, and IV medications and fluids. If changes occur during the study period, documentation of drug dosage, frequency, route, and date should also be recorded.

The investigator or qualified designee will review prior medication use, including any protocol-specified washout requirement, and record prior medication taken by the subject within 30 days before the first dose of investigational product and 30 days after the last dose of investigational product should be recorded. Concomitant medications administered after 30 days after the last dose of investigational product should be recorded if related to any serious AEs (SAEs) and AEs of special interest as defined in Section 8.2.

5.3.1.1 *Rescue Medications and Supportive Care*

Subjects should receive appropriate supportive care measures as deemed necessary by the investigator. Suggested supportive care measures for the management of AEs with potential immunologic etiology are outlined along with the dose modification guidelines in Section 5.2.5 (Table 5). Where appropriate, these guidelines include the use of oral or intravenous treatment with corticosteroids, as well as additional anti-inflammatory agents if symptoms do not improve with administration of corticosteroids. Note that several courses of steroid tapering may be necessary as symptoms may worsen when the steroid dose is decreased. For each disorder, attempts should be made to rule out other causes such as metastatic disease or bacterial or viral

infection, which might require additional supportive care. The treatment guidelines are intended to be applied when the investigator determines the events to be related to pembrolizumab.

If a pembrolizumab-related toxicity requires > 0.5 mg/kg of prednisone equivalent, then tabelecleucel should be held until the steroids are tapered to below 0.5 mg/kg.

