8 ADVERSE EVENTS

An AE is any untoward medical occurrence in a patient or clinical investigation subject administered a pharmaceutical product and which does not necessarily have to have a causal relationship with this treatment. An AE can therefore be any unfavorable and unintended sign (eg, an abnormal laboratory value), symptom, or disease temporally associated with the use of the investigational product, whether or not considered related to the investigational product [19].

Out of range laboratory values that are assessed as clinically meaningful per investigator's medical judgement must be reported as AEs with severity grading (see Section 8.3), even if they are asymptomatic. The investigator is responsible for reviewing all laboratory test results (either collected as per protocol or for any other reason) and determining whether an abnormal value in an individual subject is clinically meaningful. When part of a clinical condition, the underlying diagnosis should be listed as the AE in preference to the abnormal laboratory value (eg, anemia rather than low hemoglobin). If a unifying diagnosis is not available, then the sign(s)/symptom(s) must be reported as AE(s) in addition to the laboratory abnormality.

A laboratory value that is determined to be erroneous does not require reporting as an AE; however, any AE resulting from an action taken to treat a subject with an erroneous laboratory value should be reported as such (eg, an adverse reaction or worsening medical condition resulting from any clinical intervention based on the laboratory result).

Investigators must report all AE terms (ie, diseases/diagnoses, symptoms, or signs) and determine their seriousness criteria (Section 8.1) and severity grade (Section 8.3), as well as assess their relationship to the investigational product (Section 8.4).

If an AE changes seriousness criteria or severity grade, that event will be ended and a new AE with the changed seriousness criteria or severity grade will be recorded. Changes to other AE attributes (eg, causality) should be evaluated by the investigator to determine if a new event should be recorded.

Treatment-emergent AEs (TEAEs) are defined as events not present prior to the initiation of study product or any event already present that worsens in either intensity or frequency following exposure to study treatment.

An AE does not include the following:

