8.5.1 Serious Adverse Event Reporting Requirements

The sponsor must be notified immediately regarding information on any life-threatening or fatal SAE that is attributed to the investigational product by the investigator. This is to be followed by submission of written case details in eCRF and on the required paper reporting forms within 24 hours of the study site's knowledge of the event and as described in the eCRF completion guide and the safety reporting instructions in the study manual.

All SAEs, including AEs of special interest, occurring from the first dose of investigational product through 90 days following the last dose of investigational product, or through 30 days

following cessation of investigational product if the subject initiates a new non-protocol therapy for EBV⁺ NPC, whichever is shorter, must be reported to sponsor within 24 hours of the study site's knowledge of the event.

All deaths occurring within 30 days after the last dose of investigational product must be reported to the sponsor within 24 hours of the study site's knowledge of the event.

The core information when reporting an SAE is as follows:

- Subject's study identification number, principal investigator's name, and site number
- SAE information: event term, onset date, severity and causal relationship to the study product
- Seriousness Criteria: eg, death, life-threatening, in-patient hospitalization, prolongation of existing hospitalization, a persistent or significant disability or incapacity, or other important medical event
- A summary of relevant medical history, pertinent laboratory data or other test results
- The first and last dates of investigational product administration, and indication whether the investigational product was discontinued or the schedule of administration was modified
- NOTE: Care should be taken to redact any identification information (name, address, etc.) from any records being sent in to the sponsor/designee for safety review to protect subject confidentiality

In the event of an SAE, the report should be sent within 24 hours with as much information as is available at the time (including discharge summaries, autopsy reports, death certificates, or any other pertinent documentation). Supplemental information may be provided using a follow-up report and should not delay the initial report. The sponsor, or designee, may contact the investigational site to solicit additional information or to follow-up on the event.

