## **11 SAFETY ANALYSES**

### **11.1 Summary of Adverse Events**

MedDRA version 24.0 or later will be used to code AEs to a system organ class (SOC) and a PT within the SOC. The National Cancer Institute Common Terminology Criteria for Adverse Events (CTCAE) version 5.0 will be used to grade severity of AEs. For certain AEs for which CTCAE does not apply, non-CTCAE grades will be applied. The severity grade of non-CTCAE graded AEs are mapped using the following rules and then summarized together with CTCAE graded AEs: mild (grade 1), moderate (grade 2), severe (grade 3), life-threatening (grade 4), or death (grade 5). In addition, for graft-versus-host disease (GvHD), the Center for International Blood and Marrow Transplant Research (CIBMTR) consensus grading system will be used. CIBMTR grading includes an overall grade and separate grades based on rash status, bilirubin level, diarrhea status, and nausea status.

TEAEs are defined as follows:

- Any AE occurring after initiation of the first dose of study treatment through 30 days after the last administration of study treatment or
- Any pre-existing AE (ie, started prior to the first dose of study treatment) that worsened after the first dose through 30 days after the last administration of study treatment or
- Any related AE on or after first dose.

AEs occurring on the same day of the first dose of study treatment will be counted as TEAEs. AEs with complete or partial missing start/end dates will be all considered as treatment-emergent unless

- The partial start date is clearly after the 30 days of the last dose of study treatment. For example, last dose date + 30 days is in November and the AE start date is in the next January with the day missing.

or

- The partial end date is clearly before the first dose date of study treatment. For example, the first dose date is in March while the AE end date is in February with the day missing.

Imputation rules for partial missing dates may be applied to TEAE start/end dates, as described in Section 7.3.

All the AEs collected in this study (whether or not treatment-emergent) will be listed; TEAEs will be summarized as follows:

- Overall Summary of AE including
  - Any TEAEs
  - TEAEs with worst grade  $\geq 3$
  - Fatal TEAEs
  - Serious TEAEs
  - TEAEs leading to any study treatment discontinuation
  - TEAEs leading to any study treatment interruption

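### SAP 11.3 ends the concomitant-medication window at the last dose, 30 days before the protocol's collection window and the SAP's own safety windows

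*SAP*

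**What the plan says.** SAP 11.3 states that "A concomitant medication is any medication except study treatment taken during the treatment period". It then counts every medication unless one of two exclusions applies: the drug clearly ended before the first dose, or "The complete or partial medication start date is clearly after the last dose of study treatment". The SAP does not define the treatment period. What SAP 6.1 defines is a treatment exposure period, which runs from Study Day 1 to 30 days after the last administration of either product.

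Protocol 5.3.1 asks for medication taken from 30 days before the first dose "and 30 days after the last dose of investigational product should be recorded". Later medication is recorded only if it relates to a serious adverse event (SAE) or an adverse event of special interest (AESI).

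For adverse events, SAP 11.1 treats the following as treatment-emergent: "Any AE occurring after initiation of the first dose of study treatment through 30 days after the last administration of study treatment". It adds pre-existing events that worsen in that period, and related events with no end date. The laboratory summaries in SAP 11.2.1 and 11.2.2 also stop 30 days after the last dose. Protocol 8.5.1 sets a longer collection period for serious events: "All SAEs, including AEs of special interest, occurring from the first dose of investigational product through 90 days following the last dose of investigational product". This shortens to 30 days if a new NPC therapy is started.

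**The concern.** The concomitant-medication table is read beside the adverse event tables to see what treatment the toxicities required. The two should cover the same days, and here they do not. Protocol 5.2.3 withdraws any subject with a DLT from both products. If that toxicity begins between doses, the last dose is already in the past when treatment for it starts. The event enters the TEAE and DLT tables, while the drug is collected and then excluded by rule. SAP 11.3 names no listing of concomitant medications, so the SAP gives such a drug no planned output unless it is a subsequent anti-NPC therapy.

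This matters because characterizing safety is a primary objective. The study also stopped after Phase 1B with 12 subjects, and SAP 3.2 limits the efficacy summary to response rate. The safety tables are therefore a large part of what the final report will offer.

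**Working it through.** The plan gives no figure to reproduce. The check compares time windows, counted in days after the last dose of either product, because SAP 6.1 defines study treatment as tabelecleucel and/or pembrolizumab.

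**Upper bounds**

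| Item | Source | Bound |
|---|---|---|
| Medications tabulated | SAP 11.3 | +0 |
| Medications collected (general rule) | Protocol 5.3.1 | +30 |
| Treatment exposure period | SAP 6.1 | +30 |
| TEAEs, any causality | SAP 11.1 | +30 |
| Laboratory summaries and abnormalities | SAP 11.2.1, 11.2.2 | +30 |

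Gap for medications = 30 − 0 = 30 days. SAP 11.3 is the outlier against the protocol and against three other parts of the SAP.

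**Rules applied day by day**

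| Day after last dose | Drug started that day: collected? | Tabulated? | Adverse event that day: TEAE? |
|---|---|---|---|
| 0 | yes | yes | yes |
| 1 | yes | no | yes |
| 15 | yes | no | yes |
| 30 | yes | no | yes |
| 31 | only if tied to an SAE or AESI | no | only if related |

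The mismatch covers Days 1 to 30.

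**Illustration (hypothetical dates).** The last tabelecleucel dose is on Day 8. A DLT begins on Day 10, and a drug to treat it is first given the same day. Onset is 10 − 8 = 2 days after the last dose, so the event is a TEAE and enters the DLT table. The drug's start is also 2 days after the last dose, so SAP 11.3 excludes it.

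**Size per subject.** 1/12 = 8.3 percentage points, if all 12 enrolled subjects received at least one dose. This is the weight of any single subject here. It does not estimate how many subjects are affected.

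**Adverse events on the same scale**

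- Non-serious events: collected to +30, and later if at least possibly related (Protocol 8.5); the SAP window is the same. Gap = 0 days.
- SAEs and AESIs judged related: the SAP sets no end date. Gap = 0 days.
- SAEs and AESIs judged unrelated: collected to +90, treatment-emergent to +30. Gap = 90 − 30 = 60 days, unless new NPC therapy shortens collection to 30 days.

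**The case against.** *On medications.* A table of concomitant drugs can reasonably stop when dosing stops, and the loss is partial. A drug started on the day of the last dose is counted, for example one given for an infusion reaction. So is a drug with a partial date that is not clearly later. The clock runs from the last dose of either product, so a drug given for pembrolizumab toxicity is counted if tabelecleucel is given on or after the day it starts. The table is by preferred term only, so even with a longer window it would not link a drug to the toxicity it treated. All of this limits the size of the problem. None of it explains why this one window differs from the SAP's other safety windows and from the period over which the protocol collects the data.

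A reader might infer that all treatment of DLTs is lost. The documents do not support that. To say that every drug started after the last dose is excluded only restates the rule, and says nothing about how many treatments start then.

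*On adverse events.* A reader might also infer that the 30-day TEAE window wrongly drops late serious events. Protocol Section 8 sets no end date ("Treatment-emergent AEs (TEAEs) are defined as events not present prior to the initiation of study product"), 8.5.1 collects to 90 days, and 5.2.5.1 warns that immune-related events can appear months after pembrolizumab. That reading goes too far. SAP 11.1 follows the general rule in Protocol 8.5: all events to 30 days, and those at least possibly related after that. Late related events stay in the tables, and Protocol 8.4 sets a low threshold, since a relationship that cannot be excluded is possibly related. This takes the word related in the SAP's TEAE definition to include possibly related, as its related-event summaries do. Every collected event is listed, and all deaths are listed with the primary cause summarized. A 90-day window for serious events beside 30 days for the rest would put two definitions into one overview table. It could also bring in complications of progression, which Protocol 8.5 requires to be reported as adverse events. The 60 of 90 days (67%) is a share of calendar time, not of events.

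**Conclusion.** The medication mismatch is real and should be corrected. SAP 11.3 stops at the last dose, while the protocol's collection and the SAP's exposure, TEAE and laboratory windows run 30 days longer. The consequence is confined to one descriptive table. It omits drugs first started on Days 1 to 30 after the last dose, including those treating an event that ended both products and is itself tabulated. No DLT count or response rate changes. How many subjects are affected depends on the timing of onset and treatment, which the documents do not give.

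The TEAE definition is not an error. What remains is narrower: non-fatal SAEs and AESIs judged unrelated, with onset on Days 31 to 90, are collected but appear only in the all-event listing, in no serious-event or AESI summary. Closing that gap is optional.

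**What to change.** In SAP 11.3:

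1. Change the exclusion so that it applies only when the start date is clearly later than last dose of study treatment + 30 days.
2. Tie the treatment period to the treatment exposure period in SAP 6.1.
3. State that anti-NPC therapy started within those 30 days stays in the subsequent-therapy summary and does not enter the concomitant-medication table.

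The cost is a wording change and one date cut in programming, with no new data. The downside is that the table will include some drugs started after dosing ended, and a footnote can say so. Drugs recorded after Day 30 because they relate to an SAE or AESI would still fall outside the table; a short listing would cover them.

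Optional, and not a correction: add a supplementary table or listing of all SAEs and AESIs collected through the Protocol 8.5.1 window, whatever the judged relationship, leaving the 30-day TEAE definition unchanged.

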#### **11.4 Other Safety Summaries**

The results of the screening serum pregnancy test will be listed. In the event of any pregnancy reported while on-treatment or during follow-up, the relevant dates and outcome will be listed.

Descriptive statistics for vital signs will be summarized with observed value, change from baseline and percentage change from baseline by scheduled assessment time points. A listing will be provided for all vital signs data collected during the study.

ECOG performance status scores will be summarized by baseline score and worst postbaseline score.

#### **APPENDIX: SUMMARY OF LAB TESTS**

---

##### **Atara Biotherapeutics, Inc.**

The information contained in this document is confidential and proprietary information of Atara Biotherapeutics, Inc. It may not be disclosed in whole or in part without prior written consent of Atara Biotherapeutics, Inc.

Lab Test	Lab Test with CTCAE Grading	Summary of Abnormality & Shift Table	Summary of Lab Test Value by visit
LEUKOCYTES	decreased	Y	Y
PLATELETS	decreased	Y	Y
ABSOLUTE NEUTROPHIL	decreased	Y	Y
ABSOLUTE LYMPHOCYTE	increased and decreased	Y	Y
LACTATE DEHYDROGENASE (LDH)			Y
HEMOGLOBIN	decreased	Y	Y
ABSOLUTE MONOCYTES			Y
ABSOLUTE EOSINOPHILS			Y
ABSOLUTE BASOPHILS			Y
CREATININE	increased	Y	Y
TOTAL BILIRUBIN	increased	Y	Y
ASPARTATE AMINOTRANSFERASE (AST)	increased	Y	Y
ALANINE AMINOTRANSFERASE (ALT)	increased	Y	Y
ALKALINE PHOSPHATASE (ALK)	increased	Y	Y
